**Statistical methods, data analysis**

X square test or Fisher exact test will be carried out for statistical analysis to compare rates of total complications between the two groups and rates of pancreatitis, bleeding, stent migration and perforation.

Wilcoxon Mann-Withney test will be used for comparison of means between 2 continuous variables. A single-tailed P value of less than 0,05 is considered significant.

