## 1 Summary

Title	A PROSPECTIVE, RANDOMIZED, MULTICENTER STUDY COMPARING SEMS PLACEMENT WITH AND WITHOUT BILIARY SPHINCTERECTOMY IN PATIENTS WITH MALIGNANT BILIARY OBSTRUCTION
Study coordinator: [name] Protocol identifying number	ES vs noES-1
Protocol version date	Version 3 (06.07.15)
Background and rationale	
Placement of biliary self expanding metal stent (SEMS) is indicated when malignant common bile duct obstruction is encountered [1].
 
Currently, there is still controversy regarding the use of endoscopic sphincterotomy (EST) before the placement of biliary stents. EST may facilitate insertion of self expandable metal stent (SEMS) and also help avert the development of pancreatitis from stent-related occlusion of the pancreatic duct. On the other hand, ES is also independently associated with pancreatitis, bleeding, and perforation. [2-5].
 
Latest European guidelines indicate that EST is not necessary for inserting single plastic or metal biliary stents [1], nevertheless a more recent meta analysis showed that ES may decrease the rate of PEP [5].

Population and patient selection criteria	All the patient referred for endoscopic retrograde cholangiopancreatography (ERCP) due to malignant bile duct obstruction.
Study design and study duration	Prospective randomized, multicenter study. 18 months.
Description of study treatment/product/intervention	
All the patients will be randomly assigned to undergo ERCP with (Group A) or without (Group B) ES before biliary SEMS placement.
 
All the endoscopic procedures will be performed by experienced endoscopist in the endoscopy suite.
 
All the procedure will be conducted under deep sedation.
 
SEMS placed will be fully covered.

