**Objectives**

To assess the need for EST before SEMS placement in patients with malignant bile duct obstruction.

To evaluate immediate (periprocedural) and delayed (30 days) post ERCP complications including pancreatitis, SEMS migration, bleeding and perforation.

A sample size analysis to detect superiority at 5% significance level and a power of 80% showed that 500 patients had to be enrolled in each group.

Continuous variables such age will be reported in terms of their mean and range, and t-test will be done to test their main difference.

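### No primary endpoint is named among five complication comparisons that can point in opposite directions, so the result that decides the need for EST is left open

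*Combined protocol and SAP*

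**What the plan says.** The statistical methods section puts five comparisons in one sentence: "X square test or Fisher exact test will be carried out for statistical analysis" is followed by "to compare rates of total complications between the two groups and rates of pancreatitis, bleeding, stent migration and perforation". One criterion covers them all: "A single-tailed P value of less than 0,05 is considered significant".

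The Objectives section states the study question, "To assess the need for EST before SEMS placement in patients with malignant bile duct obstruction", and then lists the complications without ranking them: "To evaluate immediate (periprocedural) and delayed (30 days) post ERCP complications including pancreatitis, SEMS migration, bleeding and perforation". The sample size, stated per group, is given in the same section: "A sample size analysis to detect superiority at 5% significance level and a power of 80% showed that 500 patients had to be enrolled". No endpoint, event rate or difference is attached to it.

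The rationale in section 1 (Summary) describes effects in both directions. EST may help prevent pancreatitis caused by the stent blocking the pancreatic duct, but "ES is also independently associated with pancreatitis, bleeding, and perforation". It closes on post-ERCP pancreatitis (PEP): "nevertheless a more recent meta analysis showed that ES may decrease the rate of PEP".

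Nowhere in the available text is an endpoint called primary, a testing order given, or an adjustment for multiple tests described. Total complications is not defined as a count of events or as patients with at least one event.

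**The concern.** The trial asks one question, whether EST is needed before stenting, and plans five tests that could each be read as its answer. By the plan's own rationale they may disagree: less pancreatitis with EST, more bleeding, and little net change in the total. One report could then stress the pancreatitis result and conclude that EST is needed. Another could stress bleeding and conclude the opposite. A third could stress the total and conclude that it makes no difference. Each would follow the plan as written, and the choice could be made with the results in hand. No later analysis can repair that.

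Two consequences can be put in numbers. If one significant result out of five is enough, the error rate exceeds the stated 5%. And the difference that 500 per group can detect depends on the endpoint, which is not given.

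**Working it through.** **Inputs from the plan:** 500 per group, 5% level, 80% power (Objectives); single-tailed 0.05, chi-square or Fisher, five comparisons (statistical methods). **Assumed:** every event rate, because the documents give none.

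**Step 1: the plan's own figure.** For two proportions at one-sided 5% and 80% power,

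n = [1.645·√(2p̄(1−p̄)) + 0.842·√(p₁(1−p₁)+p₂(1−p₂))]² / (p₁−p₂)², with p̄ the mean of p₁ and p₂.

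For 15% vs 9.82%: (0.767 + 0.391)² / 0.0518² = 1.341 / 0.002683 ≈ 500. But 9% vs 5% gives 503, 5% vs 2.09% gives 499 and 2% vs 0.32% gives 502. Two-sided, 7.5% vs 3.5% gives 509. Many pairs fit, so 500 can be neither reproduced uniquely nor used to work out which endpoint was meant.

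**Step 2: upper reference.** Five independent tests at 0.05 give 1 − 0.95⁵ = 22.6%; four give 1 − 0.95⁴ = 18.5%. The true figure is lower than 22.6% because the total overlaps with its components, and because Fisher's test rejects less often than 5% when events are few.

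**Step 3: simulation with no true difference.** 200,000 trials per row, 500 per arm, four independent complications, total = any of the four, single-tailed 0.05 in one fixed direction. Chance of at least one significant result of five:

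| Pancreatitis / bleeding / migration / perforation | Uncorrected chi-square | Fisher |
|---|---|---|
| 2 / 0.5 / 1 / 0.3% | 19.3% | 8.5% |
| 4 / 1 / 2 / 0.5% | 19.8% | 11.2% |
| 5 / 2 / 3 / 1% | 20.0% | 13.3% |
| 8 / 3 / 5 / 1% | 19.8% | 13.8% |
| 10 / 5 / 5 / 2% | 19.8% | 15.1% |

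Total complications tested alone: 5.0% with chi-square, 3.5–4.2% with Fisher.

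**Step 4: cross-check by hand.** In a separate simulation at 5/2/3/0.5%, Fisher rejected in 3.8%, 2.9%, 3.5% and 1.2% of trials for the four components. Then 1 − 0.962 × 0.971 × 0.965 × 0.988 = 10.9%. Adding the total brought the simulated figure to 12.1%, so the total adds only about one point.

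**Step 5: sensitivity.**
- Using Fisher only where expected counts are low gives about 12–20%.
- With correlated complications (latent correlation 0.6), 4/1/2/0.5% gives 18.4% (chi-square) and 10.4% (Fisher); 10/5/5/2% gives 17.9% and 13.7%.
- If bleeding truly differs, the chance of a false result on at least one of the other three components is 14.2–14.4% with chi-square (1 − 0.95³ = 14.3%) and 7.6–10.3% with Fisher, over rates of 4/1/2/0.5% to 10/5/5/2%.

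**Step 6: opposing effects, an illustration.** Assume true rates with EST vs without of 3% vs 6% for pancreatitis, 3% vs 1% for bleeding, 3% vs 3% for migration and 1% vs 0.5% for perforation.
- Total with EST: 1 − 0.97 × 0.97 × 0.97 × 0.99 = 9.6%.
- Total without: 1 − 0.94 × 0.99 × 0.97 × 0.995 = 10.2%.

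Here each component is tested in the direction the rationale suggests, unlike Step 3. By exact enumeration (chi-square / Fisher), pancreatitis is significant in favour of EST in 75% / 70% of trials and bleeding against EST in 75% / 67%. The total is significant in neither direction in 89% / 91%.

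**The case against.** The strongest reply is that the sentence reads naturally as total complications first and then a breakdown by type, which is ordinary safety reporting. On that reading the lead comparison has an error rate of about 3.5–5% and nothing is inflated. This stands as a plausible intention. But being listed first is not a designation, one significance criterion covers all five, and neither the sample size nor the objective is linked to the total. If that was the intention, one sentence would settle it.

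Four further points stand and limit the claim.
- The 8–20% is conditional on accepting any one significant result, a rule found nowhere in the documents, and all the rates behind it are assumed.
- The top of the range needs uncorrected chi-square even for rare events such as perforation, where Fisher would be usual; the plan gives no rule for choosing.
- Step 6 is a reason not to assume that the total should be primary, since it can hide real and opposite effects. The rationale closes on pancreatitis, which is at least as plausible a candidate.
- The available text is a summary, so what is shown is absence from that text.

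The missing sample-size assumptions are a separate weakness. They matter here only because they would have shown which endpoint was meant.

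**Conclusion.** The point holds and should be fixed before analysis. Five comparisons share one significance rule, none is primary, and the plan's rationale allows them to conflict. The result that answers the question about EST is therefore open to choice after the fact.

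If any one significant result were taken as the answer, the false-positive chance is about 8–20% instead of 5%: 8–15% with Fisher throughout and 19–20% with uncorrected chi-square. This rests on 500 per arm, no true difference, one fixed direction, independent components, and assumed rates from 2/0.5/1/0.3% to 10/5/5/2%.

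Three stronger readings are not supported.
- A reader might infer that the trial's error rate is 8–20%. The plan does not say that any single significant result decides, so the figure shows what the silence permits.
- A reader might infer that the trial is underpowered. Without an endpoint and rates, the 80% can be neither confirmed nor refuted.
- A reader might infer that 500 per group could not reliably detect even the complete removal of a 1% complication. That is true with Fisher (56% power) but not with uncorrected chi-square (88%), which the plan also allows.

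**What to change.** In the Objectives and statistical methods sections, before any comparative data are seen:

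1. Name as the single primary endpoint the one on which the 500 per group was based, and state its assumed rates. If it was total complications, define it as the proportion of patients with at least one complication up to 30 days. If it was pancreatitis, say so.
2. Test it once at the stated 5% level, and state that the conclusion on the need for EST rests on it.
3. Report the other four comparisons as secondary, as risk differences with 95% confidence intervals, with no claim of significance unless adjusted for multiplicity (for example by Holm's method).
4. If 500 per group does not give 80% power for the named endpoint, restate the power or the detectable difference rather than enrol more patients.

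The change is to wording only: no extra data or patients, and the primary test keeps its level. One-sided versus two-sided testing is a separate matter and need not be settled for this fix. There are two costs. An unadjusted secondary P value just under 0.05 can no longer be claimed as positive. And if a composite is chosen, its components must be shown beside it, because opposite effects can cancel, as in 9.6% vs 10.2% above.

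### Does it matter that the plan gives both a t-test and a Wilcoxon-Mann-Whitney test for continuous variables, and calls the second a comparison of means?

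*Combined protocol and SAP*

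**What the plan says.** The document has two sentences on continuous variables.

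- Objectives: "Continuous variables such age will be reported in terms of their mean and range, and t-test will be done to test their main difference". The difference meant is presumably that in means.
- Statistical methods, data analysis: "Wilcoxon Mann-Withney test will be used for comparison of means between 2 continuous variables".

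Neither sentence is limited to normal or to skewed data, and neither test is named as the main one with the other as a sensitivity analysis. Age is the only continuous variable mentioned anywhere.

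The complication outcomes are handled separately: "X square test or Fisher exact test will be carried out for statistical analysis to compare rates of total complications between the two groups", and the same tests serve the individual complications. The significance rule is "A single-tailed P value of less than 0,05 is considered significant".

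**The concern.** Read together, the two sentences give two tests for what seems to be one task, a comparison of means between groups, with nothing to choose between them. Where the tests disagree, an analyst could report whichever P value was preferred, and the false-positive rate would rise above its nominal level.

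The rank-test sentence is also wrong as written. The Wilcoxon-Mann-Whitney test asks whether values in one group tend to exceed those in the other. It bears on means only under an added assumption, such as a pure shift in location, which the plan does not state. A rank-test P value printed beside a difference in means could therefore be significant when the means are equal, or the reverse. If a treatment conclusion rested on a continuous outcome, this would deserve correction.

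**Working it through.** **1. Which analyses the two sentences reach.**

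| Variable named in the plan | Type | Test assigned |
|---|---|---|
| Total complications | rate | chi-square or Fisher exact |
| Pancreatitis, bleeding, stent migration, perforation | rate | chi-square or Fisher exact |
| Age | continuous, baseline | t-test by name; the rank-test sentence names no variable |

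No continuous outcome is named. The only overlap that can be shown from the text is a baseline comparison.

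**2. Sample size.** The plan states "500 patients had to be enrolled in each group" but gives no event rates, so the figure cannot be reproduced. At 80% power and without continuity correction it fits many assumed pairs of rates, for example 10% against about 5.8% (one-sided 5%) or about 5.3% (two-sided 5%). Since the named outcomes are rates, neither test for continuous data enters a calculation of this kind.

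**3. What each test assumes when there is no difference.**

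- t-test: mean of A = mean of B.
- Wilcoxon-Mann-Whitney: distribution of A = distribution of B. It has power when P(A > B) + ½P(A = B) departs from ½.

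Randomisation gives a baseline variable the same distribution in both arms. Both null hypotheses then hold, and both tests have close to their nominal level at 500 per group.

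**4. Size of the discrepancy when the arms share one distribution** (simulation, 500 per arm, alpha 0.05, assumed distributions).

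| Assumed variable | Disagree, two-sided | Disagree, one-sided |
|---|---|---|
| Normal, mean 70, SD 11 (age-like) | 1.8% | 1.5% |
| Moderately skewed | 3.3% | 2.0% |
| Lognormal(0, 1), strongly skewed | 6.2% | 5.9% |

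If an analyst took whichever test was significant, the false-positive rate would be (rate of t + rate of rank test + disagreement) / 2. For the age-like case, two-sided, with about 5% for each test, this is (5 + 5 + 1.8) / 2 = 5.9%. For the strongly skewed case, the simulated rate was 7.9% two-sided and 8.0% one-sided.

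**5. When the tests part company.** Take a lognormal(0, 1) arm against a normal arm with the same mean and SD, 1.65 and 2.16. The rank test rejected in 60% of trials (two-sided), and the Welch t-test in about 5% (4.8% in 4,000 trials, 5.0% in 3,000). This confirms that the rank test is not a test of means, but it is not a model of this trial:

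- The arms differ in shape, which randomisation rules out for a baseline variable.
- About 22% of the normal arm lies below zero, since −1.65 / 2.16 = −0.76 and Φ(−0.76) ≈ 0.22. Age cannot behave in this way.
- At the plan's one-sided threshold, the same setting gives 71% in one direction and 0.03% in the other, so 60% is not an error rate of this plan.

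**The case for a change.** The strongest case for a change is that the two sentences cover continuous variables in general, not age alone. If a continuous variable measured after randomisation were later reported, procedure time for example, the arms could differ and the choice of test could matter. With an assumed lognormal variable (log-SD 0.8) and a 10% shift, the two tests disagreed on significance in about 23% of simulated trials. The usual reading, a t-test for roughly normal data and a rank test otherwise, is not written down. Even under that reading, calling the rank test a comparison of means would be wrong, and a mean with a range would suit skewed data poorly. Two sentences would put this right at no cost.

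The description of the test and the absence of a rule stand as criticisms of the wording. The consequence does not. The plan names no continuous outcome, so the 23% applies to an analysis it does not contain. For age, a P value after randomisation tests a hypothesis known to be true, so a choice between two such P values cannot alter a conclusion about sphincterotomy. The sentences also need not conflict: one gives age as its example and the other names no variable, so they may be meant for different variables. Using Welch's form of the t-test, replacing the range with an SD, or omitting baseline P values would be matters of reporting convention and would change no result the trial relies on.

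**Conclusion.** No change to the plan is needed. The gap is an unwritten selection rule together with loose English, and analysts ordinarily fill it by using the t-test for variables summarised by means and the rank test for clearly skewed ones. The comparisons of complications and the planned 500 per group are unaffected. For an age-like baseline variable, the choice of test changes nominal significance in roughly 1.5% to 1.8% of trials, and no treatment claim follows from that result either way.

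This rests on three assumptions: the outcomes are those the plan names, all of them rates; age is compared between the groups as randomised; and the simulated distributions, which do not come from the documents, are reasonable stand-ins. If a continuous outcome were added to support a treatment claim, its test would need to be fixed in advance.

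### The only significance rule is single-tailed P < 0.05 with no direction fixed, so a difference either way can be declared significant at about a 10% false-positive rate

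*Combined protocol and SAP*

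**What the plan says.** The section Statistical methods, data analysis sets the threshold: "A single-tailed P value of less than 0,05 is considered significant". No other threshold for the analyses appears, and no tail is named. The same section gives the tests for the binary outcomes: "X square test or Fisher exact test will be carried out for statistical analysis to compare rates of total complications between the two groups", and likewise for pancreatitis, bleeding, stent migration and perforation.

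Under Objectives the aim is "To assess the need for EST before SEMS placement in patients with malignant bile duct obstruction". The sample-size statement there is "to detect superiority at 5% significance level and a power of 80% showed that 500 patients had to be enrolled in each group". It does not say which arm is to be superior, or whether the 5% is one- or two-sided.

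The background in section 1 (Summary) argues in both directions:
- For sphincterotomy: it may "help avert the development of pancreatitis from stent-related occlusion of the pancreatic duct", and "a more recent meta analysis showed that ES may decrease the rate of PEP".
- Against it: "ES is also independently associated with pancreatitis, bleeding, and perforation", and "Latest European guidelines indicate that EST is not necessary for inserting single plastic or metal biliary stents".

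**The concern.** A one-sided comparison of two proportions is legitimate when the direction is fixed beforehand and there is a reason to disregard a result the other way. Here neither condition is met. The background expects opposite effects on the same endpoint, pancreatitis, and for total complications nothing says which arm should win. Nothing in the plan prevents the tail from being chosen after the data are seen. If that happens, the 5% in each tail adds up to 10%.

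The wording is also ambiguous for the chi-square test. Single-tailed could mean a directional P, which is half the usual value. It could also mean the ordinary chi-square P, which is already an upper-tail area of the chi-square distribution and covers both directions of difference. The two readings differ by a factor of two, so two analysts following the text could disagree on whether the same data are significant.

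Finally, because the sidedness of the 5% in the sample-size statement is not given, the reader cannot tell whether the 80% power belongs to the test that will be run.

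**Working it through.** **Inputs from the plan.** 500 per group, 5% significance level and 80% power (Objectives); chi-square or Fisher's exact test and single-tailed P < 0.05 (Statistical methods, data analysis). **Assumed:** a common event rate of 2-20% in both arms, because the plan gives no rates and no target difference.

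**1. The plan's own figure.** Without rates or a difference, 500 per group can be neither reproduced nor refuted. What can be computed is the higher rate detectable with 500 per group and 80% power (normal approximation, pooled variance under the null):

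| Lower-arm rate (assumed) | One-sided 5% | Two-sided 5% |
|---|---|---|
| 2% | 4.86% | 5.32% |
| 5% | 9.01% | 9.60% |
| 10% | 15.21% | 15.95% |
| 15% | 21.04% | 21.86% |

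**2. False-positive rate.** Nominally, 0.05 + 0.05 = 0.10 if either direction counts. The exact rate is the sum, over all 501 × 501 outcomes of two independent Binomial(500, r) counts, of the probability of each outcome that the rule rejects:

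| Common rate r | Chi-square, single-tailed, either direction | Chi-square, one fixed direction | Chi-square, two-sided 0.05 | Fisher, single-tailed, either direction | Fisher, one fixed direction | Fisher, 0.025 each side |
|---|---|---|---|---|---|---|
| 2% | 9.94% | 4.97% | 4.97% | 6.22% | 3.11% | 3.13% |
| 5% | 9.96% | 4.98% | 4.88% | 7.30% | 3.65% | 3.59% |
| 10% | 10.00% | 5.00% | 4.96% | 7.99% | 4.00% | 3.92% |
| 15% | 9.99% | 5.00% | 4.96% | 8.36% | 4.18% | 4.06% |
| 20% | 10.08% | 5.04% | 4.98% | 8.48% | 4.24% | 4.16% |

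Chi-square here is uncorrected. Halving the Yates-corrected P gives the same either-direction figures as Fisher over this range. Outside it, Fisher in either direction gives 2.4% at a rate of 0.5%, 4.6% at 1% and 8.9% at 50%. All figures are per test and do not include multiplicity across total complications and the four components.

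**3. A result that changes status.** Take 50/500 (10.0%) against 69/500 (13.8%). The pooled rate is 119/1000 = 0.119, and the standard error is √(0.119 × 0.881 × 2/500) = 0.02048. Then z = 0.038/0.02048 = 1.856. With the Yates correction, z = (0.038 − 0.002)/0.02048 = 1.758.

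| Test | Single-tailed P | Two-sided P |
|---|---|---|
| Chi-square, uncorrected | 0.032 | 0.064 |
| Chi-square, Yates | 0.039 | 0.079 |
| Fisher | 0.039 | 0.078 |

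All three tests are significant single-tailed and not significant two-sided. The same holds for 50 against 68 and 50 against 70.

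**4. Power.** If 500 was derived one-sided at 5%, the standardised difference is 1.645 + 0.842 = 2.487. At two-sided 0.05, power for that difference is Φ(2.487 − 1.960) = Φ(0.527) = 0.701. Restoring 80% needs 500 × ((1.960 + 0.842)/2.487)² = 635 per group. If 500 was derived two-sided, 80% stands.

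**The case against.** The strongest reply is that the inflation is conditional. The plan is silent on direction, which is weaker than permission to declare either one. With one direction fixed, the error is about 5.0% (chi-square) or 3.1-4.2% (Fisher), and one-sided 0.05 with a justified, prespecified direction would control it. That is correct as arithmetic. But the plan fixes no direction, and nothing in it says that a result in one direction would be disregarded.

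A direction might be inferred: the question is whether sphincterotomy is needed, the aim is superiority, and the background closes on the meta-analysis in its favour. The same background cites harms of sphincterotomy, including pancreatitis, and a guideline that it is not necessary. The inference is not secure enough to stand in for a stated hypothesis.

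Three limits do stand:
- If single-tailed means the ordinary upper-tail chi-square P, that test holds its 5% and only a one-sided Fisher test could inflate. The 10% is therefore the worst reading.
- The Fisher range of 6.2-8.5% depends on the assumed rates. For components occurring at 1% or less, Fisher stays below 5% even when either direction counts.
- The example that works under all three tests covers only 68 to 70 events against 50. At 71, the uncorrected chi-square is already significant two-sided (0.042). The disagreement is about significance, not about which arm did better.

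The 5% in the sample-size statement and the single-tailed 0.05 are compatible if both are one-sided. No contradiction is shown, only that the reader cannot tell.

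**Conclusion.** The concern holds. The rule governs every comparison, including total complications, and leaves the tail open in a trial whose own rationale expects effects both ways. It allows a difference with a two-sided P of up to 0.10 to be reported as significant whichever arm it favours. Under that use, the false-positive rate is about double the intended 5% for the uncorrected chi-square test, and raised to a lesser degree for Fisher's test unless events are rare. This rests on 500 per group, on assumed common event rates of 2-20%, and on either direction being open to declaration, which the text does not exclude. Whether the stated 80% power is affected depends on how the 500 was derived, which only the sponsor can say. The rule should be corrected before analysis.

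**What to change.** In Statistical methods, data analysis, replace the sentence with a rule that a two-sided P value below 0.05 is considered significant, using the ordinary two-sided chi-square or Fisher P. This holds the error at 5% or below per test at the assumed rates, whichever arm does better, and removes the ambiguity about the chi-square tail. One-sided 0.025 with a stated and justified direction would also control the error, but the rationale as written does not support choosing a direction.

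In Objectives, add whether the 5% behind 500 per group was one- or two-sided:
- If two-sided, 80% power stands and nothing else changes.
- If one-sided, either restate the power as about 70% for the same difference, or keep 80% and restate the detectable difference. Under assumed lower-arm rates, 5% against 9.0% becomes 5% against 9.6%, and 10% against 15.2% becomes 10% against 16.0%.

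The cost is one sentence and one clause, with no extra patients. Only keeping 80% power for a difference that was sized one-sided would require more, about 635 per group.
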